#### **10.1.3.1 On-site Visit 12 (Week 39)**

The following procedures will be performed at this visit:

- Measurement of body weight
- Vital signs. After 5 minutes resting, seated SBP, DBP, and HR will be assessed 3 times with at least 1 minute between each measurement (see [Appendix C](#) for details)
- Abbreviated physical examination (the abbreviated physical examination should focus on cardiac and respiratory systems, as well as any areas important for assessment of AEs, if necessary)
- Instruction on DKA symptoms and basic GU hygiene and hydration (see [Appendix B](#)) is provided
- Patient diary is collected/reviewed and a new diary is dispensed. Instructions/training are provided as needed
- IRT to be notified IMP for re-supply
- IMP is dispensed
- IMP accounting and compliance for double-blind IMP
- Concomitant medications are assessed
- Fasting SMBG is assessed.
- The following laboratory testing (by the central laboratory):
  - Fasting plasma glucose
  - HbA1c
  - Fructosamine
  - Clinical chemistry (including amylase, lipase, uric acid) and hematology
  - Cystatin C
  - NT-proBNP
  - Fasting lipids
  - Urine pregnancy testing for WOCBP
  - Urinalysis (dipstick and microscopy)

- Additional laboratory testing at this visit:
  - PK (plasma concentration samples for sotagliflozin and sotagliflozin-3-O-glucuronide)
- Patients are evaluated for glycemic rescue (see [Section 8.2](#))
- Evaluate for 50% increase in creatinine
- AEs/SAEs/AESI/EOSI and hypoglycemia (if any) are reported
- Patients are instructed to return to the site in the fasting state
- Patients should be reminded to record the time of study drug intake on the day before their next visit
- For accountability and compliance purposes, patients are instructed to return to the site with all their used, in-use and not used treatment kits(s).

#### **10.1.3.2 On-site Visit 13 (Week 52 – end of treatment)**

The following procedures will be performed at this visit:

- Measurement of body weight
- Vital signs. After 5 minutes resting, seated SBP, DBP, and HR will be assessed 3 times with at least 1 minute between each measurement (see [Appendix C](#) for details)
- Complete physical examination
- Diet and exercise instruction
- Instruction on DKA symptoms and basic GU hygiene and hydration (see [Appendix B](#)) is provided
- IRT to be notified of EOT
- Patient diary is collected/reviewed and a new diary is dispensed. Instructions/training are provided as needed
- IMP accounting and compliance for double-blind IMP
- Concomitant medications are assessed
- Fasting SMBG is assessed
- 12-lead ECG
- The following laboratory testing (by the central laboratory):
  - Fasting plasma glucose
  - HbA1c
  - Fructosamine
  - Clinical chemistry (including amylase, lipase, uric acid) and hematology
  - Cystatin C
  - NT-proBNP

- Fasting lipids
- Urine pregnancy testing for WOCBP
- Urinalysis (dipstick and microscopy)
- Collection of home urine for albumin, protein, creatinine, calcium, phosphorus, magnesium, glucose and albumin:creatinine ratio.
- Additional laboratory testing at this visit:
  - Pre-dose PK (plasma concentration sample for sotagliflozin and sotagliflozin-3-O-glucuronide); an additional blood sample will be collected 3 hours after IMP administration for the assessment of creatinine (for eGFR) and for assessing plasma concentration of sotagliflozin and sotagliflozin-3-O-glucuronide.
  - Markers of intestinal transit and absorption (vitamins B6, B12, K, E, and A, serum folate, and ferritin)
  - Markers of bone and calcium metabolism (serum calcium, serum 25-hydroxyvitamin D, serum 1,25-dihydroxyvitamin D, serum magnesium, serum phosphorus, serum iPTH, markers of bone resorption [serum NTX, serum  $\beta$ -CTX-1], and bone formation [serum P1NP]), osteocalcin, and ALP
- Patients are evaluated for glycemic rescue (see [Section 8.2](#))
- Evaluate for 50% increase in creatinine
- AEs/SAEs/AESI/EOSI and hypoglycemia (if any) are reported
- Patients are instructed to return to the site in the fasting state for Visit 14 (Week 56).

#### **10.1.4 Post-treatment follow-up period**

The post-treatment follow-up period will include an on-site visit 4 weeks after the last dose of IMP.

##### **10.1.4.1 On-site follow-up Visit 14 (Week 56 - end of study)**

The following procedures will be performed at this visit:

- Measurement of body weight
- Vital signs. After 5 minutes resting, seated SBP, DBP, and HR will be assessed 3 times with at least 1 minute between each measurement (see [Appendix C](#) for details)
- Abbreviated physical examination (the abbreviated physical examination should focus on cardiac and respiratory systems, as well as any areas important for assessment of AEs, if necessary)
- IRT to be notified of EOS
- Glucose meter to be collected
- Patient diary is collected/reviewed

- Concomitant medications are assessed
- Fasting SMBG is assessed
- The following laboratory testing (by the central laboratory):
  - Clinical chemistry (including amylase, lipase, uric acid) and hematology
  - Cystatin C
- AEs/SAEs/AESI/EOSI and hypoglycemia (if any) are reported
- The patient is instructed to schedule future follow-up with their own personal physician.

## **10.2 DEFINITION OF SOURCE DATA**

### **10.2.1 Source data to be found in patient's file**

Evaluations recorded in the e-CRF must be supported by appropriately signed source documentation related but not limited to the following:

- Agreement and signature of ICF with the study identification
- Study identification (name)
- Patient number, confirmation of randomization, treatment batch number, dates and doses of study medication administration
- Medical, surgical, diabetes history, including information on:
  - Demography, inclusion and exclusion criteria
  - Last participation in a clinical trial
  - Contraception method for WOCBP
  - Previous and concomitant medication.
- Dates and times of visits and assessments including examination results
- Vital signs, height, body weight, laboratory reports, investigation results (eg, ECG traces, imaging reports)
- Adverse events and follow-up:
  - In case of SAE, the site should file in the source documents at least copies of the hospitalization reports and any relevant examination reports documenting the follow-up of the SAE
- Date of premature treatment discontinuation (if any) and reason
- Date of premature study discontinuation (if any) and reason
- Nursing notes
- Dietician's notes
- Physician's notes.

### **10.2.2 Source data verification requirements for screen failures**

For screen failure patients, the following source data must be verified: patient's identification details, the informed consent signed by the patient, the study identification (name), dates of study visits, and the main reasons for screen failure.

## **10.3 HANDLING OF PATIENT TEMPORARY OR PERMANENT TREATMENT DISCONTINUATION AND OF PATIENT STUDY DISCONTINUATION**

The IMP should be continued whenever possible. In case the IMP is stopped, it should be determined whether the stop can be made temporarily; permanent IMP discontinuation should be a last resort. Any IMP discontinuation should be fully documented in the e-CRF. In any case, the patient should remain in the study and followed for the remainder of the study to collect vital safety status and endpoint data.

### **10.3.1 Temporary treatment discontinuation with investigational medicinal product**

Temporary treatment discontinuation may be considered by the Investigator because of suspected AEs.

Lower extremity complications (such as skin ulcers, infection, osteomyelitis, and gangrene) requiring treatment should lead to temporary discontinuation of IMP.

If at any visit after randomization up to Week 8 there is a rise in creatinine level (ie, >50% increase from baseline level, where baseline level is defined as the mean of creatinine values obtained at Screening and Randomization) or if at any visit after Week 8 there is a rise of >50% above the mean of creatinine values from last 2 visits, the Investigator should ensure that no reasonable explanation exists for creatinine increase.

The IMP should be stopped for 2 weeks.

Re-initiation of treatment with the IMP will be done under close and appropriate clinical/and or laboratory monitoring once the Investigator has considered according to his/her best medical judgment that the responsibility of the IMP in the occurrence of the concerned event was unlikely to be related to the IMP and that the selection criteria for the study are still met (refer to [Section 7.1](#) and [Section 7.2](#)).

If at creatinine recheck the patient has returned to the below threshold then IMP will be restarted at a reduced dose (ie, dose reduced via IRT to 200 mg for those randomized to 400 mg; maintained at 200 mg for those randomized to 200 mg). Since the IMP received is blinded, patients must return to the site and IRT will be contacted for IMP re-initiation.

It is in the interest of the patient to monitor blood glucose during the temporary discontinuation period, therefore regular determination of SMBG is to be performed and documented (see [Section 9.2.1.7](#)).

For all temporary treatment discontinuations, duration should be recorded by the Investigator in the appropriate pages of the e-CRF when considered as confirmed.

Temporary treatment discontinuation decided by the Investigator corresponds to more than 1 dose not administered to the patient.

Use of any other anti-hyperglycemic medication during the time of temporary treatment discontinuation (ie, insulin during a hospitalization) is recorded as concomitant medication with the name and doses recorded in the e-CRF.

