	
if at any visit after Week 8 there is a rise of >50% above the mean of creatinine values from the previous 2 visits, the Investigator should ensure that no reasonable explanation exists for creatinine increase and in particular the following causes:
 
 
• Medications that increase creatinine
 
• Decrease in cardiac output
 
• Obstructive uropathy
 
• Urinary tract infection
 
• Volume depletion
 
 
If addressing these causes does not reduce the creatinine level below the above stated threshold, the investigational medicinal product (IMP) will be stopped for 2 weeks. If at creatinine recheck the patient has returned to below the threshold, then IMP will be restarted at a reduced dose (ie, dose reduced via interactive response technology (IRT) to 200 mg for those randomized to 400 mg; maintained to 200 mg for those randomized to 200 mg, and to placebo for those randomized to placebo). If the creatinine does not return to below the threshold, the IMP will be permanently discontinued but the patient will be asked to continue attending all study visits.
 
Patients will be randomly assigned 1:1:1 to 1 of 3 treatment groups:
 
 
A. Placebo;
 
B. Sotagliflozin 200 mg
 
C. Sotagliflozin 400 mg
 
 
The HbA1c and FPG results will be masked to study sites and patients after randomization and until study end. To prevent partial unblinding, UGE and urine glucose:creatinine ratio (UGCR) results will be also masked to study sites and patients.
 
Additionally, urinalysis by dipstick will not include the measurement of urine glucose. Quantitative urine glucose, albumin, calcium, and creatinine will be measured separately at selected on-site visits by the central laboratory.
 
Early Termination
 
If a patient discontinues treatment with IMP early during the Treatment Period, the patient will have a Premature end of treatment (EOT) Visit, and a Follow-up Visit 4 weeks after the last dose of IMP. In addition, every effort will be made to have all patients return to the site at the time corresponding to their scheduled visits, particularly the Weeks 26 and 52 visits.
 
If the patient does not agree to site visits, they will be contacted by telephone to enquire about safety status, particularly at the time of the initially scheduled end of study.
 
The study design is presented graphically in Section 1.1.

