#### 8.1.1 Dose reduction

The dose maintenance will be handled according to the renal function assessed by the creatinine measurement throughout the study. If at any visit after randomization there is a rise in creatinine level (see details in Section 10.6.2), the Investigator should ensure that no reasonable explanation exists for creatinine increase. Sites will be notified by central laboratory alert if a patient has a >50% increase from Baseline level or >50% above the mean of creatinine values from the last 2 visits, where Baseline level is defined as the mean of creatinine values obtained at Screening and Randomization. The IMP should be stopped for 2 weeks. If at creatinine recheck the patient

has returned to the below threshold then IMP will be restarted at a reduced dose (ie, dose reduced via IRT to 200 mg for patients randomized to 400 mg, maintained to 200 mg for patients randomized to 200 mg, and to placebo for those randomized to placebo). Since IMP received is blinded, patients must return to the site and IRT will be contacted for this IMP re-initiation. Dose reduction can only be obtained at on-site visit by IRT. If the creatinine does not return to below the threshold, the IMP will be permanently discontinued but the patient will be asked to continue attending all study visits.

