## **10.6.2 Deterioration of renal function**

Patients will be monitored throughout the double-blind Treatment Period for signs of deterioration in renal function (eg, decrease in eGFR or increase in creatinine as defined below) as well as other routine clinical and laboratory findings (see Study Flowchart, [Section 1.2](#)). If at any visit after randomization up to Week 8 there is a rise in creatinine level (ie,  $> 50\%$  increase from baseline level, where baseline level is defined as the mean of creatinine values obtained at Screening and Randomization) or if at any visit after Week 8 there is a rise of  $> 50\%$  above the mean of creatinine values from last 2 visits, the Investigator should ensure that no reasonable explanation exists for creatinine increase and in particular the following causes:

- Medications that increase creatinine
- Decrease in cardiac output
- Obstructive uropathy
- Urinary tract infection
- Volume depletion

If addressing these causes does not reduce the creatinine level below the above stated threshold, the IMP will be stopped for 2 weeks. The dose will be handling according to the renal function assessed by the creatinine measurement throughout the study and as detailed in [Section 10.3.1](#).

If the creatinine dose not return to below the threshold, then the IMP will be permanently discontinued but the patient will be asked to continue attending all study visits.

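### After a >50% creatinine rise, the 2-week IMP stop is conditional in the synopsis and Section 10.6.2 but has no stated exception for a corrected cause in Sections 8.1.1 and 10.3.1

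*Protocol*

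**What the plan says.** Four places in the protocol govern the response to a creatinine rise above 50%.

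- **Synopsis, study design.** The investigator looks for five named causes (medication, reduced cardiac output, obstruction, urinary infection, volume depletion). Then: "If addressing these causes does not reduce the creatinine level below the above stated threshold, the investigational medicinal product (IMP) will be stopped". The stated length of the stop is 2 weeks.
- **Section 10.6.2.** The same list, followed by: "If addressing these causes does not reduce the creatinine level below the above stated threshold, the IMP will be stopped for 2 weeks". Dose handling is then referred to Section 10.3.1.
- **Section 8.1.1.** It opens with "If at any visit after randomization there is a rise in creatinine level (see details in Section 10.6.2", asks for the explanation check, describes the central laboratory alert, and then gives the 2-week stop as a sentence of its own.
- **Section 10.3.1.** After the same rise, "the Investigator should ensure that no reasonable explanation exists for creatinine increase". The next statement is "The IMP should be stopped for 2 weeks".

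On restart, Section 10.3.1 has the "dose reduced via IRT to 200 mg for those randomized to 400 mg" and "maintained at 200 mg for those randomized to 200 mg". The synopsis and Section 8.1.1 add that placebo patients restart on placebo. Restart requires creatinine to be below the threshold at recheck. Section 10.3.1 alone also requires the investigator to judge that the event was unlikely to be due to IMP and that the selection criteria are still met.

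Flow-chart footnote e, repeated in SAP Appendix E, foresees extra creatinine recheck visits at two-week intervals from Visit 8. SAP 2.4.3.1 counts patients with a dose interruption or reduction due to creatinine increase.

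**The concern.** Take a patient randomized to 400 mg whose creatinine rises by more than 50% during a urinary infection, and whose creatinine falls below the threshold once the infection is treated. A site working from the synopsis or Section 10.6.2 has no reason to stop IMP, and the patient stays on 400 mg. A site working from Section 8.1.1 or 10.3.1 finds an instruction to stop for 2 weeks and then to restart at the lower dose. Both sites can say that they followed the protocol.

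The dose change falls only on the arm that carries the primary hypothesis. The SAP count that should describe such changes mixes two rules. Patients with the same event are also handled differently while their creatinine is raised.

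**Working it through.** The point is textual, so the four places are set side by side.

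| Place | Explanation check | Condition on the 2-week stop | Where it sends the reader |
|---|---|---|---|
| Synopsis | Yes, five causes listed | Only if addressing the causes fails | No other stop rule |
| 10.6.2 | Yes, five causes listed | Only if addressing the causes fails | 10.3.1, for dose handling |
| 8.1.1 | Yes, no list | None stated | 10.6.2, for details of the rise |
| 10.3.1 | Yes, no list | None stated | Not back to 10.6.2 |

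**Where they agree and differ.**

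1. No cause is found, or correction leaves creatinine above the threshold: all four stop IMP.
2. A cause is corrected and creatinine falls below the threshold: the synopsis and 10.6.2 do not trigger a stop. Sections 8.1.1 and 10.3.1 have no branch for this case and, as written, stop IMP for 2 weeks.

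The conflict is confined to case 2.

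**What differs in case 2.** One reading gives uninterrupted IMP, the other a 14-day gap. Afterwards, the 200 mg and placebo arms restart unchanged. In the 400 mg arm the dose becomes 200/400 = one half, provided the restart conditions are met.

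**The recheck.** Footnote e supplies two-weekly creatinine visits from Visit 8. It does not say whether they belong to the period of correcting a cause or to the hold, and it does not cover alerts before Visit 8.

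**Size.** The documents give no rate of creatinine alerts and no share with a correctable cause, so the number of patients in case 2 cannot be derived. An assumed range shows how sensitive the primary comparison could be.

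- Plan's own figure (Protocol 11.1: difference 0.5%, SD 1.2%, two-sided 0.05, 92 per group): n = 2 × (1.960 + 0.842)² × (1.2/0.5)² = 90.4, so 91. Power at 92 is 80.7% (normal) or 80.3% (t). The stated figure of at least 80% reproduces and is not in dispute.
- Assumption: a share f of the 400 mg arm shows the 200 mg effect because of the reading followed. Scaling from the Phase 2b results in Protocol 4.3, (0.52 − 0.14)/(0.93 − 0.14) = 0.38/0.79 = 0.48, and 0.48 × 0.5% = 0.24%.
- Diluted difference: 0.5 − f × (0.5 − 0.24).

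| Assumed f | Difference (%) | Power at 92 per group |
|---|---|---|
| 2% | 0.495 | 79.9% |
| 5% | 0.487 | 78.6% |
| 10% | 0.474 | 76.4% |
| 20% | 0.448 | 71.7% |

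This ignores the effect of the 2-week gap itself and the timing of the event. A reduction after Week 26 cannot touch the primary endpoint. The table is an illustration, not an estimate.

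**The case against.** The best defence is that the four places say one thing at different lengths. Sections 8.1.1 and 10.3.1 both require the explanation check before the stop, and that check would be idle if its result changed nothing. Section 8.1.1 points to 10.6.2, so it can be read as a summary of the conditional rule. Section 10.6.2 sends only dose handling to 10.3.1. The opening of Section 10.3 favours continuing IMP where possible, which fits the conditional text.

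Much of this stands. A reader might infer that 8.1.1 and 10.3.1 stop IMP on any rise without further thought. They do not, because the check comes first. What is missing is any statement of what follows when the check succeeds. The defence also goes some way for 8.1.1. It does not repair 10.3.1, which is where 10.6.2 sends the investigator for dosing, which states the stop without the condition, and which has no pointer back. A general preference for continuing does not override a specific instruction to stop that follows it in the same section.

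A reader might also infer that, on the conditional reading, IMP simply runs on until the next scheduled visit. Footnote e and the provision for optional visits in Section 10.1 do not support that. They leave unclear only how the recheck relates to the hold.

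**Conclusion.** The inconsistency is real and can be read directly from the text. When correcting a cause brings creatinine below the threshold, the protocol supports two courses: IMP unchanged, or a 2-week hold. In the 400 mg arm only, the hold leads to restart on 200 mg if the restart conditions are met. Exposure in the primary comparison arm and the SAP 2.4.3.1 count depend on which section is followed.

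Three stronger readings go beyond the documents.

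- Not every alert is affected, and not every alert with a correctable cause. The places diverge only when correction succeeds.
- The primary analysis is not shown to be biased. Treatment is blinded and efficacy is analyzed as randomized (Protocol 11.3.1, SAP 2.3.1). The effect is variable exposure, and so possible dilution, of unknown size.
- No planned analysis is invalidated by differences between sites. The SAP count is descriptive and by treatment group, and center is not in the efficacy models (SAP 2.5.6).

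Confidence is high for the textual conflict. Its effect on power rests wholly on the assumed shares above.

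**What to change.** Reconcile the synopsis, Sections 8.1.1, 10.3.1 and 10.6.2, and flow-chart footnote e into one rule. State it in full in one section and have the others refer to it without restating it. The rule should make clear when the hold starts, what happens when a cause has been found and corrected, and how the two-weekly recheck visits relate to the hold. The restart conditions should be in the same place, since Section 10.3.1 currently adds two that the other sections lack and leaves out the placebo arm. Which rule applies is for the sponsor's clinical team, and nothing here favours one.

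The cost is a protocol wording amendment and a memo to sites. No assessment is needed beyond the rechecks already foreseen. The SAP 2.4.3.1 count can stay as it is, because it refers to interruption under the protocol and would then have a single meaning.

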### **7.2.2 Exclusion criteria related to the diabetes or CKD history and treatment**

- E 13. Type 1 diabetes mellitus.
- E 14. HbA1c <7% or >11% measured by the central laboratory at Screening.
- E 15. Oral antidiabetic agent or insulin use where the dose was not stable for 8 weeks before randomization (ie, oral agents changed during past 8 weeks or total daily basal insulin dose increased or decreased by more than 20% during the past 4 weeks).
- E 16. Use of a selective SGLT2 inhibitor (eg, canagliflozin, dapagliflozin, or empagliflozin) within 12 months prior to the trial.
- E 17. History of DKA or nonketotic hyperosmolar coma within 12 weeks prior to the Screening Visit.
- E 18. History of severe hypoglycemia that resulted in unconsciousness, coma, or hospitalization within 6 months prior to the Screening Visit.
- E 19. CKD stage 5: defined as chronic dialysis or eGFR < 15.
- E 20. Reversible causes of renal failure such as obstruction within 6 months of Screening.

E 21. Renal disease that required treatment with immunosuppressive therapy within the last 12 months, or renal transplant or initiation of chronic dialysis within 4 weeks prior to the Screening Visit or expected to occur during the study duration.

E 22. History of hereditary glucose galactose malabsorption or primary renal glucosuria.

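### Protocol 10.3.1 gives two restart rules after a creatinine hold, one with causality and eligibility conditions and one on creatinine alone, and nothing says which governs

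*Protocol*

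**What the plan says.** Protocol 10.3.1 covers every temporary stop: suspected adverse events, lower-extremity complications and creatinine rises. After the instruction to hold treatment for two weeks, it gives two restart provisions in consecutive paragraphs.

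- **Conditional provision.** The product is re-initiated once the investigator considers it unlikely to have caused the event and "that the selection criteria for the study are still met", with a reference to Sections 7.1 and 7.2. Inclusion criterion I 01 requires an MDRD eGFR of at least 15 and below 30. Exclusion criterion E 19 reads "CKD stage 5: defined as chronic dialysis or eGFR < 15".
- **Creatinine-only provision.** "If at creatinine recheck the patient has returned to the below threshold then IMP will be restarted at a reduced dose". Neither causality nor eligibility is mentioned.

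The second provision stands alone elsewhere. The synopsis says "If at creatinine recheck the patient has returned to below the threshold, then IMP will be restarted at a reduced dose", and 8.1.1 says of the recheck that a patient who "has returned to the below threshold then IMP will be restarted at a reduced dose". The stated alternative in 8.1.1 is: "If the creatinine does not return to below the threshold, the IMP will be permanently discontinued". Section 10.6.2 refers back to 10.3.1 for dose handling. The list of reasons for permanent discontinuation in 10.3.3 does not include an eGFR below 15.

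The threshold changes with time. Up to Week 8 it is a ">50% increase from baseline level, where baseline level is defined as the mean of creatinine values obtained at Screening and Randomization". Later it applies "if at any visit after Week 8 there is a rise of >50% above the mean of creatinine values from last 2 visits".

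**The concern.** A patient whose creatinine has fallen back under the threshold, but not to baseline, can satisfy the creatinine-only provision and fail the conditional one. The first then directs a restart and the second withholds it. These patients have had the largest creatinine rises, and some are near an eGFR of 15, which SAP 2.4.4.3 counts as end-stage renal disease when sustained for at least 30 days.

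The restart decision also affects the statistics. It changes exposure duration and the treatment-emergent period. It also fixes whether a patient counts as having discontinued before Week 26. Under the preferred method in SAP 2.4.4.1, that status decides whether a missing Week 26 value is imputed from discontinued patients in the same arm who still have an endpoint value, or by wash-out from placebo patients still on treatment. It also feeds the count of such retrieved dropouts. Fewer than 5 in any arm switches the whole method to copy-reference imputation.

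**Working it through.** The documents give no figure on this point, so there is none to reproduce. The check asks when the two provisions disagree.

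**Inputs.** Creatinine exponent of -1.154 in the MDRD formula (SAP 2.5.1). Lower eGFR limit of 15 and eligible range of 15 to 30 (Protocol 7.1, 7.2.2). Threshold of 1.5 times the reference creatinine (Protocol 10.3.1).

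**Formula.** Within one patient the age, sex and race terms cancel, so eGFR at recheck = baseline eGFR × (creatinine ratio)^-1.154. I take baseline eGFR as the value from baseline creatinine, and assume that the threshold which triggered the hold is the one applied at recheck.

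**Up to Week 8**

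- 1.5^-1.154 = 0.6263, so creatinine just under threshold means eGFR has fallen by 37.4%.
- Baseline eGFR at which this gives exactly 15: 15 / 0.6263 = 23.95.
- Width of range exposed: (23.95 - 15) / 15 = 8.95 / 15 = 59.7%.
- Example, baseline eGFR 20: eGFR reaches 15 at a ratio of (20/15)^(1/1.154) = 1.28, and just under 1.50 it is 20 × 0.6263 = 12.5. A recheck between 1.28 and 1.50 times baseline meets the creatinine-only provision and fails the eGFR criterion.
- With better recovery the cut-off falls. A recheck at 1.4 times baseline gives 15 × 1.4^1.154 = 22.1, and at 1.2 times baseline 18.5.

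**After Week 8.** Let m be the mean creatinine of the last two visits as a multiple of baseline. The cut-off is 15 × (1.5m)^1.154. The values of m are assumptions, since the documents give none.

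| m (assumed) | Cut-off, baseline eGFR | Share of range width |
|---|---|---|
| 0.9 | 21.2 | 41% |
| 1.0 | 23.95 | 60% |
| 1.1 | 26.7 | 78% |
| 1.2 | 29.6 | 97% |
| 1.22 or more | 30 or above | 100% |

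**Causality condition.** This needs no arithmetic. Under the synopsis and 10.6.2, treatment is held only after the listed alternative causes have been addressed without bringing creatinine under the threshold. If creatinine then falls during the two-week hold, that points towards the product rather than away from it. The conditional provision asks for a judgment that the product is unlikely to be responsible, whereas the creatinine-only provision directs a restart at reduced dose on the same facts. This can happen at any eGFR.

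**The case against.** The strongest reply is that the text can be read without contradiction. Section 10.3.1 is general, so the creatinine paragraph could be the specific rule that overrides the general one, in line with 8.1.1 and the synopsis. Or the paragraphs could be cumulative: stop, conditions for re-initiation, then dose. Each reading is coherent, but they give opposite answers for the patients described above and the protocol chooses neither. This confirms the ambiguity.

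A second reply is that many selection criteria are tied to Screening, so re-applying them literally during treatment is strained. That has some force. E 19, however, carries no such wording, and 10.3.1 itself asks whether the criteria are still met.

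Other parts of the reply stand and limit the point:

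- A reader might infer that the protocol compels a restart at eGFR below 15. It does not, because 10.3.3 lets the investigator stop permanently if continuing would harm the patient, or for an inter-current condition possibly caused by the product.
- A reader might infer that most patients are exposed. The 60% is a width of range up to Week 8, and the documents give no eGFR distribution. An eGFR conflict needs a rise of more than 50%, persistence after other causes are addressed, a hold, and then only partial recovery. A patient who returns to a baseline of 15 or more meets both the eGFR and the creatinine tests.
- A reader might infer that the primary result is at risk. Week 26 HbA1c is used as observed even after discontinuation (Protocol 11.4.2.1, SAP 2.4.4), so restart status does not remove observed values.

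**Conclusion.** The point holds as an unresolved conflict between stated restart rules. Up to Week 8, a baseline eGFR below about 24 leaves room for creatinine under the threshold with eGFR below 15 if recovery is partial. After Week 8 the cut-off moves with the last two visits, from about 21 to the top of the range for reference means of 0.9 to 1.22 times baseline. The causality condition adds a second conflict that does not depend on eGFR.

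The calculation rests on the MDRD exponent, on reading I 01 and E 19 as applying at restart, and on a fixed threshold at recheck. The number of patients is unknown. That sites would in fact act differently is a possibility the text leaves open and the documents do not establish. In the primary analysis the effect is limited to exposure and to the imputation of missing Week 26 values. This warrants correction because it concerns patients with a safety signal and is cheap to settle, not because it threatens the main conclusion.

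**What to change.** Reconcile Protocol 10.3.1 with 8.1.1, 10.6.2, 10.3.3 and the synopsis, so that a single restart rule after a creatinine hold applies at all sites. The text should say explicitly whether the causality judgment and the selection criteria, including the eGFR limit, apply to that restart, and what follows when creatinine is under the threshold but another condition fails. Section 10.3.3 should be aligned at the same time, since it measures the rise from baseline throughout, whereas 10.3.1 changes the reference after Week 8. Which rule to adopt is a clinical decision for the sponsor, and none is proposed here.

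The cost is a protocol clarification, with no added visit, test or procedure.
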